# 8.3 Adverse Events and Serious Adverse Events

#### 8.3.1 Definition of Adverse Events (AE)

Adverse event means any untoward medical occurrence associated with the use of an intervention in humans, whether or not considered intervention-related (21 CFR 312.32 (a)).

# 8.3.2 Definition of Serious Adverse Events (SAE)

An adverse event (AE) or suspected adverse reaction is considered "serious" if, in the view of either the investigator or sponsor, it results in any of the following outcomes: death, a life-threatening adverse event, inpatient hospitalization or prolongation of existing hospitalization, a persistent or significant incapacity or substantial disruption of the ability to conduct normal life functions, or a congenital anomaly/birth defect. Important medical events that may not result in death, be life-threatening, or require hospitalization may be considered serious when, based upon appropriate medical judgment, they may jeopardize the participant and may require medical or surgical intervention to prevent one of the outcomes listed in this definition. Examples of such medical events include allergic bronchospasm requiring intensive treatment in an emergency room or at home, blood dyscrasias or convulsions that do not result in inpatient hospitalization, or the development of drug dependency or drug abuse.

#### 8.3.3 Classification of an Adverse Event

# 8.3.3.1 Severity of Event

For adverse events (AEs) not included in the protocol defined grading system, the following guidelines will be used to describe severity.

- Mild Events require minimal or no treatment and do not interfere with the participant's daily activities.
- Moderate Events result in a low level of inconvenience or concern with the therapeutic measures. Moderate events may cause some interference with functioning.
- Severe Events interrupt a participant's usual daily activity and may require systemic drug therapy or other treatment. Severe events are usually potentially life-threatening or incapacitating. Of note, the term "severe" does not necessarily equate to "serious".

# 8.3.3.2 Relationship to Study Intervention

All adverse events (AEs) must have their relationship to study intervention assessed by the clinician who examines and evaluates the participant based on temporal relationship and his/her clinical judgment. The degree of certainty about causality will be graded using the categories below. In a clinical trial, the study product must always be suspect.

- **Related** The AE is known to occur with the study intervention, there is a reasonable possibility that the study intervention caused the AE, or there is a temporal relationship between the study intervention and event. Reasonable possibility means that there is evidence to suggest a causal relationship between the study intervention and the AE.
- **Not Related** There is not a reasonable possibility that the administration of the study intervention caused the event, there is no temporal relationship between the study intervention and event onset, or an alternate etiology has been established.

OR

• **Definitely Related** — There is clear evidence to suggest a causal relationship, and other possible contributing factors can be ruled out. The clinical event, including an abnormal laboratory test result, occurs in a plausible time relationship to study intervention administration and cannot be explained by concurrent disease or other drugs or chemicals. The response to withdrawal of the study intervention (dechallenge) should be clinically plausible. The event must be pharmacologically or phenomenologically definitive, with use of a satisfactory rechallenge procedure if necessary.

• **Probably Related** — There is evidence to suggest a causal relationship, and the influence of other factors is unlikely. The clinical event, including an abnormal laboratory test result, occurs within a reasonable time after administration of the study intervention, is unlikely to be attributed to concurrent disease or other drugs or chemicals, and follows a clinically reasonable response on withdrawal (dechallenge). Rechallenge information is not required to fulfill this definition.

- Potentially Related There is some evidence to suggest a causal relationship (e.g., the event occurred within a reasonable time after administration of the trial medication). However, other factors may have contributed to the event (e.g., the participant's clinical condition, other concomitant events). Although an AE may rate only as "possibly related" soon after discovery, it can be flagged as requiring more information and later be upgraded to "probably related" or "definitely related", as appropriate.
- Unlikely to be related A clinical event, including an abnormal laboratory test result, whose temporal relationship to study intervention administration makes a causal relationship improbable (e.g., the event did not occur within a reasonable time after administration of the study intervention) and in which other drugs or chemicals or underlying disease provides plausible explanations (e.g., the participant's clinical condition, other concomitant treatments).
- **Not Related** The AE is completely independent of study intervention administration, and/or evidence exists that the event is definitely related to another etiology. There must be an alternative, definitive etiology documented by the clinician.

# 8.3.3.3 Expectedness

The Study PI will be responsible for determining whether an adverse event (AE) is expected or unexpected. An AE will be considered unexpected if the nature, severity, or frequency of the event is not consistent with the risk information previously described for the study intervention.

# 8.3.4 Time Period and Frequency for Event Assessment and Follow-Up

The occurrence of an adverse event (AE) or serious adverse event (SAE) may come to the attention of study personnel during study visits and interviews of a study participant presenting for medical care, or upon review by a study monitor.

All AEs including local and systemic reactions not meeting the criteria for SAEs will be captured on the appropriate case report form (CRF). Information to be collected includes event description, time of onset, clinician's assessment of severity, relationship to study product (assessed only by those with the training and authority to make a diagnosis), and time of resolution/stabilization of the event. All AEs occurring while on study must be documented appropriately regardless of relationship. All AEs will be followed to adequate resolution. Any medical condition that is present at the time that the participant is screened will be considered as baseline and not reported as an AE. However, if the study participant's condition deteriorates at any time during the study, it will be recorded as an AE.

Changes in the severity of an AE will be documented to allow an assessment of the duration of the event at each level of severity to be performed. AEs characterized as intermittent require documentation of onset and duration of each episode.

The Study RA or PI will record all reportable events with start dates occurring any time after informed consent is obtained until 7 (for non-serious AEs) or 30 days (for SAEs) after the last day of study participation. At each study visit, the investigator will inquire about the occurrence

of AE/SAEs since the last visit. Events will be followed for outcome information until resolution or stabilization.

# 8.3.5 Adverse Event Reporting

Plans for Reporting Serious Anticipated and Unanticipated Adverse Events Adverse events > level 3 will be reported to the IRB within 24 hours. Other adverse events will be reported to the IRB in a timely manner, using the following predefined causal relationships:

# **Attribution of Risk Categories:**

Definite: Adverse event(s) will clearly be related to investigational agent(s) or other

intervention

Probable: Adverse event(s) will likely be related to investigational agent(s)
Possible: Adverse event(s) may be related to investigational agent(s)

Unlikely: Adverse event(s) will doubtfully be related to investigational agent(s)
Unrelated: Adverse event(s) will clearly not be related to the investigational agents(s)

Monitoring for data integrity and safety will be the responsibility of the Principal Investigator, the Yale University IRB, and a Data and Safety Monitoring Board (DSMB). The DSMB will meet twice per year to review study progress. A DSMB will be used to provide additional protections for participants and to monitor progress on the study.

# 8.3.6 Serious Adverse Event Reporting

The study clinician will immediately report to the sponsor any serious adverse event, whether or not considered study intervention related, including those listed in the protocol or investigator brochure and must include an assessment of whether there is a reasonable possibility that the study intervention caused the event. Study endpoints that are serious adverse events (e.g., all-cause mortality) must be reported in accordance with the protocol unless there is evidence suggesting a causal relationship between the study intervention and the event (e.g., death from anaphylaxis). In that case, the investigator must immediately report the event to the sponsor.

All serious adverse events (SAEs) will be followed until satisfactory resolution or until the site investigator deems the event to be chronic or the participant is stable. Other supporting documentation of the event may be requested by the Data Coordinating Center (DCC)/study sponsor and should be provided as soon as possible.

The study sponsor will be responsible for notifying the Food and Drug Administration (FDA) of any unexpected fatal or life-threatening suspected adverse reaction as soon as possible, but in no case later than 7 calendar days after the sponsor's initial receipt of the information. In addition, the sponsor must notify FDA and all participating investigators in an Investigational New Drug (IND) safety report of potential serious risks, from clinical trials or any other source, as soon as possible,

but in no case later than 15 calendar days after the sponsor determines that the information qualifies for reporting.

## 8.3.7 Reporting Events to Participants

Adverse events will be reported to participants individually.

# 8.3.8 Events of Special Interest

N/A

# 8.3.9 Reporting of Pregnancy (if applicable)

Positive pregnancy results will be reported to the study participant.

# 8.4 Unanticipated Problems

# 8.4.1 Definition of Unanticipated Problems (UP)

The Office for Human Research Protections (OHRP) considers unanticipated problems involving risks to participants or others to include, in general, any incident, experience, or outcome that meets **all** of the following criteria:

- Unexpected in terms of nature, severity, or frequency given (a) the research procedures that are described in the protocol-related documents, such as the Institutional Review Board (IRB)-approved research protocol and informed consent document; and (b) the characteristics of the participant population being studied;
- Related or possibly related to participation in the research ("possibly related" means there is a reasonable possibility that the incident, experience, or outcome may have been caused by the procedures involved in the research); and
- Suggests that the research places participants or others at a greater risk of harm (including physical, psychological, economic, or social harm) than was previously known or recognized.

Additional example text, applicable for device protocols:

This definition could include an unanticipated adverse device effect, any serious adverse effect on health or safety or any life-threatening problem or death caused by, or associated with, a device, if that effect, problem, or death was not previously identified in nature, severity, or degree of incidence in the investigational plan or application (including a supplementary plan or application), or any other unanticipated serious problem associated with a device that relates to the rights, safety, or welfare of subjects (21 CFR 812.3(s)).

# 8.4.2 Unanticipated Problem Reporting

The investigator will report unanticipated problems (UPs) to the reviewing Institutional Review Board (IRB) and to the Data Coordinating Center (DCC)/lead principal investigator (PI). The UP report will include the following information:

• Protocol identifying information: protocol title and number, PI's name, and the IRB project number;

- A detailed description of the event, incident, experience, or outcome;
- An explanation of the basis for determining that the event, incident, experience, or outcome represents an UP;
- A description of any changes to the protocol or other corrective actions that have been taken or are proposed in response to the UP.

To satisfy the requirement for prompt reporting, UPs will be reported using the following timeline:

UPs will be promptly reported to the IRB of record and to the DCC/study sponsor in accordance with policy and regulatory requirements. When Children's National serves as the IRB of record, UPs should be reported to the IRB within 7 business days of the investigator becoming aware of the UP.

# 8.4.3 Reporting Unanticipated Problems to Participants

Unanticipated problems will be reported to participants individually.

# 9 - Statistical Considerations

# 9.1 Statistical Hypotheses

Aim 1: To determine differences in fronto-limbic mGluR5 availability between people with cannabis use disorder (CUD; n = 30) and healthy controls (HC; n = 30). Subjects will undergo [18F]FPEB PET neuroimaging to determine mGluR5 availability. Hypothesis 1: Frontolimbic mGluR5 availability will be higher in individuals with CUD compared with HC. Aim 2: Within CUD subjects, to examine the associations between mGluR5 availability and: (a) CUD severity; (b) impulsivity; (c) EEG; and (d) neurocognition. CUD severity and impulsivity will be determined by validated instruments. EEG outcomes (e.g., theta power, LTP) known to be sensitive to both cannabis and glutamate will be collected during tasks of verbal memory and neural plasticity (long term potentiation; LTP). Hypothesis 2: Higher mGluR5 availability will be associated with: (a) greater CUD severity (by DSM-5); (b) higher impulsivity; (c) lower theta-band power and LTP, and (d) worse performance on verbal memory. Aim 3: Within CUD subjects, to determine changes in mGluR5 availability, EEG, and neurocognition following cannabis abstinence. CUD subjects from Aim 1 will repeat PET scanning, EEG, and cognitive testing following a 28-day period of confirmed abstinence aided by contingency management. Hypothesis 3: Following cannabis abstinence: (a) mGluR5 will decrease; (b) theta power/LTP will be increased; (c) memory will improve.

# 9.2 Sample Size Considerations

# STATISTICAL DESIGN AND POWER

Frequency distributions and descriptive statistics for all variables will be computed prior to conducting analyses. If Shapiro-Wilk normality tests indicate non-normality for any continuous variable, we will compute necessary data transformations (e.g., logarithmic base 10) prior to conducting analyses. Of note, to conserve power, we will compute an average  $V_T$  value across the 6 study ROIs to be used in all PET analyses. This choice is supported by the fact that preliminary data revealed large magnitude (i.e., r's>0.80-0.95) correlations between OFC, dlPFC, amygdala and hippocampus [ $^{18}$ F]FPEB  $V_T$ . Thus, we plan to treat this set of regions as a circuit and compute a mean composite score of [ $^{18}$ F]FPEB  $V_T$  for use in analyses.

Aim 1: To determine differences in fronto-limbic mGluR5 availability between people with cannabis use disorder (CUD; n = 30) and healthy controls (HC; n = 30). Hypothesis 1: Fronto-limbic mGluR5 availability will be higher in individuals with CUD compared with HC. Power Calculations for Hypothesis 1: We approached power calculations by considering both our preliminary data and relevant and reliable literature (i.e., conducted with rigorous scientific methodologies, published in competitive, peer reviewed journals, with sufficient sample sizes) to determine the magnitudes of effect sizes that we might reasonably expect to observe in this study. No studies outside of our preliminary ones presented above (Research Strategy, Section C.1.a) have examined this topic of study specifically. However, we identified studies which examined differences in receptor availability in vivo between individuals who did and did not report use of cannabis using PET. For example, a recent examination of CB1 receptor availability in cannabis users vs. non-users showed a mean VT 15% lower (d=-1.11). Another study found 20% lower CB1 in chronic daily cannabis users relative to non-users. Based on the

information provided in each manuscript, we calculated effect sizes for group differences. Observed effect sizes for group comparisons of cannabis users vs. non-users ranged from d= -0.68 to -1.77, with a median of d=-1.11. These effect sizes are consistent with those observed in our preliminary data, which showed a large effect size associated with differences in mGluR5 availability in CB relative to healthy control individuals in the fronto-limbic circuit (d= 1.72). We will evaluate hypothesis 1 (higher mGluR5 availability in cannabis users) using univariate analysis of variance (ANOVA). Assuming  $\alpha$ =0.05 (two-tailed test) and two groups (cannabis vs. control), our proposed sample size of 60 (30 per group) will provide 81.07% statistical power to detect group differences as small as d= 0.82, which is smaller than the median effect size observed in previous literature and that observed in our preliminary data. Data Analysis for Hypothesis 1: As stated, we will conduct a univariate ANOVA to compare mean fronto-limbic [18F]FPEB  $V_T$  between the HC and cannabis groups. Groups will be carefully matched on demographic variables. However, any demographic variables that differ significantly between groups, including notably age and sex, will be considered for entry as additional fixed factors (categorical variables) or covariates (continuous variables). A significant group difference suggestive of higher mGluR5 availability in CUD subjects will be considered supportive of Hypothesis 1. We will also conduct exploratory analyses to examine betweengroup differences in mGluR5 in other regions, including those involved in affective and cognitive dysregulation (e.g., thalamus, striatum, insula), at the same significance level.

Aim 2: Within CUD subjects, to examine the associations between mGluR5 availability and: (a) CUD severity; (b) impulsivity; (c) EEG; and (d) neurocognition. Hypothesis 2: Higher mGluR5 availability will be associated with: (a) greater CUD severity (by DSM-5); (b) higher impulsivity; (c) lower theta-band power and LTP, and (d) worse performance on verbal memory. Power Calculations for Hypothesis 2: Using the same standards applied for hypothesis 1, we considered our preliminary data and conducted a literature review to determine what magnitude of correlation we could reasonably expect to see in this study between relevant variables of interest. We included studies with similar methodologies, which reported correlations between similar variables (i.e. similar EEG measures and cognitive/behavioral constructs, and an *in vivo* measurement of neuroreceptor or transporter availability in humans using PET). Examples include an unpublished study from our research group in which the correlation between mGluR5 availability and impulsivity in BPD and PTSD individuals ranged from 0.46. to 0.80 in frontal and limbic brain regions of interest (n= 56). Observed correlations ranged in magnitude from 0.21 to 0.80 (positive or negative) with a median r = 0.57. Magnitude of relevant correlations observed in our preliminary data are comparable (i.e., correlation between impulsivity and fronto-limbic mGluR5 availability, r = 0.896). We will evaluate aim 2 using correlational analyses. Using a correlation estimate of 0.55 (based on both review of the literature and our pilot data) and a two-tailed  $\alpha = 0.05$ , a priori power analysis suggested we will require a minimum n = 24 to achieve more than 80% power for the planned analysis. As we plan to conduct correlational analyses within the CUD group (n = 30), we will be adequately powered to test this hypothesis. Data Analysis for Hypothesis 2: Correlational analysis (Spearman or Pearson, as appropriate based on observed data distributions) will be used to test for associations between fronto-limbic mGluR5 availability, CUD severity, impulsivity,  $\theta$ - band power and LTP, and working memory performance. Multiple regression analyses will also be considered to control for potential confounding variables. a will be set at 0.05 for all planned correlational analyses. We will also assess for associations between mGluR5 availability and performance on

other domains as secondary/exploratory analyses, keeping significance at the same level. Significant positive correlations between fronto-limbic mGluR5, CUD severity, and impulsivity will be supportive of Hypothesis 2. Likewise, significant negative correlations between fronto-limbic mGluR5, θ- band power and LTP, and working memory performance will be considered supportive of hypothesis 2. Of note, the relationship between other relevant and clinically meaningful variables pertaining to CUD (e.g. craving, withdrawal, duration/intensity of use), and mGluR5 availability will also be examined in exploratory analyses. The influence of potentially relevant demographic variables including **age and sex will be examined.** 

Aim 3: Within CUD subjects, to determine changes in mGluR5 availability, EEG, and neurocognition following cannabis abstinence. Hypothesis 3: Following cannabis abstinence: (a) mGluR5 will decrease; (b) theta power/LTP will be increased; (c) memory will improve. Power Calculations for Hypothesis 3: Using the same standards applied for Aims 1 and 2, we considered our preliminary data and conducted a literature review to determine the magnitude of effect sizes we might reasonably expect to observe with respect to change in mGluR5, EEG, and cognition as a function of abstinence from cannabis. Values necessary to calculate associated effect sizes were not provided in the reviewed literature. For example, Hirvonen and colleagues (2012) observed a significant increase in CB1 receptor availability in cannabis users after abstinence in both the PFC and amygdala. While percent change (pre-post abstinence) could be roughly estimated from the figure provided, exact values are not available, preventing effect size estimation. We do not have preliminary data examining participants pre- and postcannabis abstinence. However, we believe that comparison of available PET data showing in vivo mGluR5 availability in current cannabis users compared with former users may be indicative of the magnitude of change we can expect to see following abstinence. Comparison of mGluR5 availability in current and former cannabis users in our preliminary sample (n= 5 per group) showed a large effect (d = -1.2). We will evaluate Hypothesis 3 using repeated measures ANOVA. Using a moderate effect size estimate of d = 0.58 at  $\alpha = 0.05$  (highly conservative relative to the noted relevant finding in our preliminary data), a priori power analysis suggested we will require n = 30 to achieve 80.13% power for the planned analysis. Data analysis for Hypothesis 3: To test Hypotheses 3, we will conduct 3 repeated measures ANOVAs to examine changes pre- and post-cannabis abstinence in n = 30 CUD subjects. Specifically, models will evaluate: (1) changes in mGluR5 availability; (2) changes in  $\theta$ -band power and coherence; (3) changes in cognition pre-post abstinence from cannabis in the CUD group. Variables that differ significantly between groups, including age and sex, will be considered for entry into the models. A statistically significant result indicative of lower mGluR5 availability following abstinence (model 1) or higher  $\theta$ - band power and coherence (model 2) and improved cognition (model 3) will be considered supportive of Hypothesis 3.

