#### **Accrual Ceiling**

Our target enrollment for study completion is 60 subjects: 30 cannabis use disorder (CUD) subjects and 30 healthy controls.

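### The Aim 1 power figure does not follow from its own inputs: 30 per group at d = 0.82 gives 87.8%, not 81.07%

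*Combined protocol and SAP*

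**What the plan says.** Section 9.2 (Power Calculations for Hypothesis 1) gives the inputs and the result together. The test is made "using univariate analysis of variance (ANOVA"), the error rate and design are "0.05 (two-tailed test) and two groups (cannabis vs. control"), and the result is that "our proposed sample size of 60 (30 per group) will provide 81.07% statistical power to detect group differences as small as d= 0.82". The plan then describes this effect as one "which is smaller than the median effect size observed in previous literature and that observed in our preliminary data"; the values given for those are a median |d| of 1.11 (range 0.68 to 1.77) and a pilot d of 1.72.

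The outcome is a single composite, the mean V_T over six regions, so alpha is not divided. Under Data Analysis for Hypothesis 1, demographic variables that differ between groups "will be considered for entry as additional fixed factors (categorical variables) or covariates (continuous variables"), but the power sentence includes none. The group size is the same elsewhere: the Accrual Ceiling in the Synopsis gives "30 cannabis use disorder (CUD) subjects and 30 healthy controls", and sections 3.1, 5.1 and 9.1 agree. Sections 9.4.1 to 9.4.3 only point back to 9.2.

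**The concern.** Sample size, effect size, alpha and test together determine the power of a two-group comparison. A power quoted to two decimals should therefore be reproducible from the inputs beside it, and this one is not.

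Two things are at stake. First, the sentence is the only justification for 30 per group in Aim 1, which tests the overall hypothesis; as it stands, a reader cannot tell whether n, d or the power is the wrong element. Second, the wording presents d = 0.82 as the limit of what the study can detect at roughly 80% power. If that limit is misplaced, a null or small result will be read against the wrong benchmark. The literature effects cited in the same paragraph start at |d| = 0.68, so the position of the limit is of some interest.

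**Working it through.** **Inputs, all from section 9.2 (Hypothesis 1):** n1 = n2 = 30; d = 0.82; two-sided alpha = 0.05; one-way ANOVA with two groups, which is equivalent to the two-sample t-test; no covariates, dropout deduction or alpha split in the power statement.

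**Attempt to reproduce 81.07%**

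- Degrees of freedom: 1 and 30 + 30 − 2 = 58. Critical F at 0.05 = 4.0069.
- Noncentrality: λ = d² × n1·n2/(n1 + n2) = 0.82² × 900/60 = 0.6724 × 15 = 10.086.
- Power = P(F(1, 58; λ = 10.086) > 4.0069) = 0.8776.
- The two-sided noncentral t with noncentrality √10.086 gives the same 0.8776. The cruder normal approximation gives 0.888.

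The stated figure is not reproduced: 87.76 − 81.07 = 6.69 points. The type II error is 100 − 87.8 = 12.2%, against the implied 100 − 81.07 = 18.9%.

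**Could a reasonable variant give 81.07%?** All at d = 0.82 unless noted.

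| Variant | Power |
|---|---|
| d anywhere from 0.815 to 0.825 (rounding) | 87.4% to 88.1% |
| 1 to 6 degrees of freedom spent on covariates | 87.7% to 87.6% |
| 10% loss in the CUD group only (27 v 30) | 85.9% |
| 10% loss in both groups (27 v 27) | 84.1% |
| One-sided test | 93.2% |
| Rank test, relative efficiency 0.955 | 86.2% |
| Rank test, worst-case efficiency 0.864 | 82.5% |
| Two-sided alpha 0.025 | 80.7% |
| 24 per group | 79.4% |
| 25 per group | 81.08% |

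The variants that come within 2 points of 81.07% either change a stated input (n or alpha) or assume a worst-case rank test that the plan does not specify; for non-normal data, section 9.2 calls for transformation.

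**Solving for d at 30 per group**

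- 80% power: d = 0.7356, i.e. 0.74.
- 81.07% power: d = 0.7458. This lies between d = 0.74 (80.5%) and d = 0.75 (81.5%), so no d given to two decimals yields exactly the stated power.

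**Possible source.** By the noncentral t, 25 per group is the smallest size that passes 80% at d = 0.82 (24 gives 79.4%, 25 gives 81.08%). By the normal approximation, 24 per group gives 81.07%. This suggests a calculation for about 48 to 50 subjects set beside the text for 60. It is an inference only; the documents never give 24 or 25 per group for Aim 1.

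**The case against.** The strongest objection is that three quantities disagree and the documents do not show which is at fault. If d was mistyped, the power is not understated; the detectable effect is overstated. This is right about the cause. It does not affect the correction, because 87.8% at d = 0.82 and 80% at d = 0.74 are both true for 30 per group whichever figure was mistyped, and the source calculation is to be checked first.

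The second objection is that the plan says dropouts are accounted for in the analytic plan (Synopsis, and sections 6.1.1 and 6.4) at an expected 10%, so an evaluable-sample allowance might lie behind the figure. It does not rescue 81.07%. Dropouts are to be replaced, the relapses in question occur after the Day 0 scan that supplies the Aim 1 data, and deducting 10% anyway still leaves 84.1% or 85.9%.

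The third objection is that nothing depends on the correction: the error is conservative, and the operative claim, that the detectable effect lies below 1.11 and 1.72, is true at 0.74, 0.75 or 0.82. This stands, and it limits the point to accuracy and traceability. It does not make the sentence correct.

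**Conclusion.** The concern holds. On the inputs printed beside it, the Aim 1 power is 87.8%, and the stated 81.07% is 6.7 points too low. The effect detectable with 80% power at 30 per group is d = 0.74, not 0.82. This rests on the unadjusted two-group ANOVA with normal data, equal variances, 30 evaluable subjects per group and two-sided alpha 0.05. Later covariate adjustment is outside the stated calculation.

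The study is not underpowered for Aim 1 on its own assumptions: 30 per group is adequate at d = 0.82, and the comparison with the literature median and the pilot effect is unaffected. The fault is that the only sample-size justification for the main hypothesis cannot be reproduced and gives the wrong detectable limit.

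**What to change.** Retrieve the source calculation and see which of n, d, alpha or power differs from the text. Then restate the sentence in section 9.2 along these lines: with 30 per group, an unadjusted two-group ANOVA at two-tailed alpha 0.05 has 87.8% power for d = 0.82, or 80% power for d = 0.74. If the source calculation used something the section does not show, such as a smaller evaluable sample or a stricter alpha, state that input and the power it gives. The comparison with the median and pilot effects can stay.

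The cost is one sentence of wording. Enrolment, procedures and analysis do not change.
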